#### 3.3 Covariates

Baseline characteristics overall and by treatment arm will be described using the list of covariates in **Table 3-1**. Balance of characteristics will be assessed using standardized differences. Given the potential unknown impact of one or more surges of Covid-19 during the enrollment and follow-up period of the study, an *a priori* decision was made to adjust for indices for acute severity of illness, predicted short-term readmission risk and multimorbidity burden as well as the presence of active Covid-19 during the index hospitalization, along with any observed additional baseline differences in participant characteristics for regression models of efficacy.

**Table 3-1.** List of candidate covariates.

| Category                              | Variables   |
|---------------------------------------|---|
| Demographic characteristics           | Age, self-reported gender, self-reported race/ethnicity   |
| Prior medical history                 | Heart failure, diabetes mellitus, chronic kidney disease, acute myocardial infarction, coronary artery bypass surgery, percutaneous coronary intervention, mitral or aortic valvular disease, atrial fibrillation or flutter, ventricular tachycardia or fibrillation, ischemic stroke or transient ischemic attack, venous thromboembolism, hypertension, dyslipidemia, current smoker, hospitalized bleed, hyperthyroidism, hypothyroidism, chronic liver disease, chronic lung disease, diagnosed depression, diagnosed dementia |
| Pre-admission vital signs             | Body mass index, systolic blood pressure  |
| Index hospitalization characteristics | length of stay, major discharge diagnosis category (MDC) based on diagnosis-related groups (DRG), laboratory-based acute physiology score version 2.0 (LAPS 2), predicted readmission risk score, comorbidity point score version 2.5 (COPS 2.5), evidence of active Covid-19 infection   |
| Inpatient laboratory values           | Hemoglobin, serum creatinine, blood urea nitrogen   |

### 3.4 Missing data

The state-of-the-art EHR at KPNC will be used to identify all hospitalizations and emergency department visits, including any that occur at non-network hospitals given that KPNC is fiscally liable for these types of urgent or emergent resource utilization. Deaths are systematically captured through EHR data (including participant proxy reporting) complemented by external state death certificate data and Social Security Administration vital status file information, with >97% estimated capture based on prior studies involving KPNC members. In addition, all participants' medical records will be manually reviewed for the occurrence of death at the end of follow-up if the research team is unable to reach the participant or their listed secondary contact(s). Thus, it is unlikely to be missing data on clinical outcomes or that data availability will be differentially available between those assigned to MTMs or Usual Care. Participants with missing data from follow-up surveys will be excluded from analyses of patient-reported outcomes.

Missing data on covariates will be described in the baseline table and imputed for use in models, as needed. If less than 5% of covariate data are missing across all covariates of interest, then missing data will be imputed using the median value of each covariate in the full sample. If more than 5% of data are collectively missing for covariates of interest, then a multiple imputation approach will be used to impute data across all covariates.

#### 3.5 Interim analysis

There are no planned interim analyses, and adjustments for multiple comparisons will not be performed.

#### 3.6 Software

All analyses will be conducted using SAS statistical software version 9.4 (SAS Institute, Cary, NC).

### 4 Efficacy analyses

### 4.1 Primary outcome: Readmission for any cause within 90 days post-discharge

The frequency and risk with associated 95% exact (Clopper-Pearson) binomial confidence intervals (CI) for participants experiencing readmission for any cause within 90 days after discharge from the index hospitalization will be reported by treatment arm. Risk differences will be calculated along with associated Wald 95% CI. Cumulative incidence curves from the cumulative incidence function will be reported descriptively without statistical testing.

The primary measure of association will be the hazard ratio (and associated 95% CI) for MTMs vs Usual Care obtained from a Cox proportional hazards model adjusted for acute severity of illness, predicted short-term readmission risk and multimorbidity burden as well as the presence of active Covid-19 during the index hospitalization, along with any observed additional baseline differences in participant characteristics in the primary analysis population.

The subdistribution hazard ratio (95% CI) for MTMs vs Usual care obtained from Fine and Gray subdistribution hazard models adjusted for acute severity of illness, predicted short-term readmission risk and multimorbidity burden as well as the presence of active Covid-19 during the index hospitalization, along with any observed additional baseline differences in participant characteristics in the primary analysis population will also be reported to examine the effect of MTMs on the cumulative incidence of hospitalizations for any cause accounting for the potential effects of a competing risk of death.

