7.4 Randomization

This study will incorporate the concept of pre-randomization (i.e., prior to obtaining informed consent and administering the intervention) in order to streamline the study workflow consistent with the pragmatic trial design. Pre-randomization will be stratified by participating KPNC medical center (i.e. participants will be pre-randomized separately within each medical center).

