9.3 Loss to Follow-up

For participant's whose status is unclear because they fail to complete study contacts without stating an intention to withdraw, the KPNC DOR research team will show due diligence by attempting to contact the participant, the participant's family and/or listed secondary contact(s), or KPNC primary treating physician. The KPNC DOR research team will also continue to monitor the participant's KPNC EHR data as agreed in the informed consent and will also document in the Appian-based study online tracking system all of the steps taken to contact the participant (i.e. dates of telephone calls, etc.). A participant should not be formally considered lost to follow-up until his/her scheduled end of study visit would have occurred. Outcome data for endpoint ascertainment should be available for all participants with active KPNC membership status.

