#### 3.2 Follow-up and censoring

Participants will be followed for 90 days after discharge for all utilization outcomes and death and will be censored the end of 90 days, loss of KPNC membership or last known contact if they are lost to follow-up.

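### The planned 90-day risk difference counts early-censored participants as event-free and forgoes adjustment already available: a small flaw that is cheap to correct

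*SAP*

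**What the plan says.** SAP 4.1 plans, for each arm, the number and proportion readmitted within 90 days with an exact binomial interval, and then the contrast: "Risk differences will be calculated along with associated Wald 95% CI". It names no handling of incomplete follow-up, no stratification and no covariates for these quantities. The next sentence covers the one absolute-risk method that allows for censoring: "Cumulative incidence curves from the cumulative incidence function will be reported descriptively without statistical testing". The risk difference is not the lead result: "The primary measure of association will be the hazard ratio (and associated 95% CI) for MTMs vs Usual Care", from a Cox model adjusted for acute severity, predicted readmission risk, multimorbidity burden and active Covid-19.

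SAP 3.2 says that participants "will be censored the end of 90 days, loss of KPNC membership or last known contact if they are lost to follow-up". Protocol 7.4 adds: "Pre-randomization will be stratified by participating KPNC medical center". SAP 3.3 confines covariate adjustment to the regression models. SAP 4.2 applies the 4.1 methods to all seven secondary clinical outcomes, and SAP 4.4 repeats them for meals alone versus meals plus counseling.

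**The concern.** A binomial proportion divides events by everyone in the arm. A participant who leaves the health plan on day 30 without a readmission stays in the denominator as if known to be event-free to day 90. The Cox and Fine-Gray models treat that same person as censored. So the only absolute effect with a confidence interval comes from the method that ignores the SAP's own censoring rule.

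It is also unclear which events count. SAP 3.2 censors at last known contact for those lost to follow-up and does not define contact. Protocol 9.3 continues record monitoring for people who miss study contacts. If a readmission after the last contact enters the binomial count but not the Cox model, the risk difference and the hazard ratio rest on different events.

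Finally, the risk difference leaves unused the randomization stratum and four covariates that are already collected and already committed to the hazard ratio.

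**Working it through.** The plan states no expected risk difference and no censoring rate, so there is no figure of its own to reproduce here. The planning values in SAP section 2 serve as inputs, and the censoring fractions are assumptions shown over a range.

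**Inputs.** From SAP section 2: 1000 per arm, a 90-day risk of 10% (source range 10-15%) taken here as the usual-care risk, and a hazard ratio of 0.68. Assumed: exponential event times, and exponential censoring independent of readmission.

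**True contrast.** MTMs risk = 1 - 0.90^0.68 = 6.91%. Risk difference = 6.91 - 10.00 = -3.09 points. Wald SE = sqrt(0.10×0.90/1000 + 0.0691×0.9309/1000) = 1.24 points.

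**What the crude proportion estimates.** Let a = -ln(1 - risk), and g = -ln(1 - c), where c is the fraction whose censoring time falls before day 90. The expected crude proportion is a/(a+g) × [1 - exp(-(a+g))]. Example, usual care with c = 5%: a = 0.1054, g = 0.0513, so 0.6726 × 0.1450 = 9.75% instead of 10%.

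| Censored, usual care / MTMs | Crude risks, usual care / MTMs (%) | Crude difference (points) | Shift (points) | Shift / SE |
|---|---|---|---|---|
| 1% / 1% | 9.95 / 6.88 | -3.07 | +0.015 | 0.01 |
| 3% / 3% | 9.85 / 6.81 | -3.04 | +0.045 | 0.04 |
| 5% / 5% | 9.75 / 6.74 | -3.01 | +0.075 | 0.06 |
| 10% / 10% | 9.50 / 6.57 | -2.93 | +0.15 | 0.12 |
| 5% / 2% | 9.75 / 6.85 | -2.91 | +0.18 | 0.14 |
| 10% / 5% | 9.50 / 6.74 | -2.76 | +0.33 | 0.26 |
| 2% / 5% | 9.90 / 6.74 | -3.16 | -0.07 | -0.06 |
| 5% / 10% | 9.75 / 6.57 | -3.19 | -0.10 | -0.08 |

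With no true effect, equal censoring gives no bias. The unequal patterns create a spurious difference of 0.15 to 0.25 points. At a 15% control risk, the top of the SAP's range, the largest shift is 0.48 points (0.33 SE). For the composite at the SAP's 20% rate and hazard ratio of 0.76, it is 0.60 points (0.35 SE).

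**Medical center.** Assume five equal centers with equal allocation. The unstratified difference is then unbiased. The stratified SE is 0.999 of the unstratified one if center risks run from 8% to 12%, and 0.993 if they run from 5% to 15%.

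**Covariates.** Randomization gives no expected bias from leaving them out. The adjusted SE is about sqrt(1 - R²) of the crude SE. For R² = 0.023 (c-statistic 0.64) that is 0.99, and for R² = 0.149 (c-statistic 0.80) it is 0.92. A chance imbalance of one SE in such a covariate shifts the crude difference by 0.20 to 0.45 points.

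**Agreement with the hazard ratio.** In 400 simulated trials per setting at a true hazard ratio of 0.68, the Wald difference and the Cox model disagreed on significance in 1% of trials with no covariate, and in 9 to 12% with a strong one (log-hazard SD 1). The signs were opposite in 1% or fewer. Adding 5% or 10% censoring did not clearly change this.

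**The case against.** The best defense is that little censoring should occur. SAP 3.4 says that "it is unlikely to be missing data on clinical outcomes" and that availability should not differ by arm. Protocol 9.3 says: "Outcome data for endpoint ascertainment should be available for all participants with active KPNC membership status". Protocol section 6 follows participants through the record to 90 days, including care outside the network, so ascertainment does not depend on the 10-week call. The adjusted hazard ratio is the primary measure, and the Fine-Gray model and the cumulative incidence curves already allow for censoring. This stands, and it is why the size is small. It does not say how someone who leaves the plan before day 90 enters the binomial risk.

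A second point also stands. If last known contact means study contact, that rule may distort the Cox model more than a crude count drawn from the full record. Switching to the cumulative incidence function without settling the rule would then bring the same censoring into the absolute effect. Nor does that function correct bias when censoring is related to readmission.

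A reader might infer more in three ways:

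- **Heavy one-sided censoring.** MTMs participants have weekly deliveries and usual care has a single call. If 20% of usual care were censored near discharge and 5% of MTMs at day 45, the crude risks would be 0.80 × 10 = 8.0% and 0.95 × 6.91 + 0.05 × 3.52 = 6.7%, a difference of -1.3. Under no effect the pattern gives 9.8 - 8.0 = +1.8 points against MTMs. Nothing in the documents supports 20%, and Protocol sections 6 and 9.3 and SAP 3.4 point the other way.
- **Bias from omitting center, covariates or competing death.** The first two cost precision only under randomization, and the Cox covariates named in SAP 4.1 do not include center either. A crude proportion with full follow-up already estimates cumulative incidence with death as a competing event. Imbalance beyond chance is possible because consent follows randomization, but adjustment for measured covariates would repair that only in part.
- **Disagreement with the hazard ratio as an error.** A crude difference and an adjusted hazard ratio estimate different things, so some disagreement is expected.

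**Conclusion.** The mismatch is real: SAP 3.2 censors before day 90, and the binomial risks and Wald difference in SAP 4.1 have no place for censored participants. Its likely effect is small. On a true difference of -3.1 points, equal censoring of 1-10% moves the estimate 0.02 to 0.15 points toward zero. An imbalance of 3 to 5 points between arms moves it by up to about 0.3 points, or 0.5 at a 15% control risk, which is at most about a third of a standard error. These figures rest on assumed censoring fractions and on censoring independent of readmission. The bias claim rests on censoring alone. Center and covariates are a matter of precision, worth under 1% of the SE for center and about 1 to 8% for covariates. The primary hazard-ratio analysis is not called into question by the crude risk difference. The undefined last-contact rule affects both measures and has to be settled first.

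**What to change.** 1. Reconcile SAP 3.2 with Protocol 9.3. Censor utilization outcomes when record capture ends (loss of membership or day 90), not at last study contact, and state that the same events feed the risk difference and the hazard ratio.
2. In SAP 4.1, 4.2 and 4.4, take the 90-day risks (30- and 60-day where those are the outcomes) and the risk difference with its 95% CI from the cumulative incidence function with death as the competing event. Use 1 minus Kaplan-Meier for death and the composite. Standardize over medical center and the four a priori covariates, with a bootstrap or influence-function interval.
3. Report the number censored, with reason and timing, by arm. Keep the crude counts and proportions as description.

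The cost is SAP wording and a little more programming. The variables are already collected, and sample size and conduct do not change. Step 1 must come before step 2.

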Study Design	discharge from the index hospitalization. Given the increasing consideration among health insurers about providing MTMs as a benefit of enrollment, and recent federal Center for Medicare and Medicaid Services' guidance allowing MTMs as a supplemental benefit in selected populations, there is a pressing need to generate robust evidence about the potential efficacy of MTMs to guide health policy and health care delivery system decision-making. This study is a remote, decentralized, randomized PCT. We will compare outcomes in 3 groups of recently hospitalized patients with a targeted, nutrition-sensitive chronic medical condition (i.e., heart failure, diabetes mellitus or chronic kidney disease): participants receiving MTMs alone, participants receiving MTMs with remotely delivered nutritional counseling, and patients receiving usual standard of care. Participants will be recruited from Kaiser Permanente (KP) Santa Rosa, Santa Clara, Oakland, San Francisco, and San Rafael Medical Centers. The Ceres Community Project (Ceres) will provide MTMs service to patients enrolled at KP Santa Rosa and San Rafael Medical Centers and Project Open Hand (POH) will provide MTMs service to patients enrolled at KP Santa Clara, Oakland and San Francisco Medical Centers.
Intervention	MTMs (with or without remotely delivered nutritional counseling) vs.
	usual care

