#### 4.3 Secondary patient-reported outcomes

The following scales will be analyzed for the targeted patient-reported outcomes:

- 1.) Change in perceived social isolation (Likert 1-5 scale: Never, Rarely, Sometimes, Often, Always)
  - a. I feel left out.
  - b. I feel that people barely know me.
  - c. I feel isolated from others.
  - d. I feel that people are around me but not with me.
- 2.) Change in perceived self-efficacy (i.e., "How confident are you that you can stick with healthful foods?" Likert 1-10 scale: ranging from Not Confident to Completely Confident)
  - a. Even if you need a long time to develop necessary routines?
  - b. Even if you have to try several times to make it work?
  - c. Even if you have to rethink your entire way of nutrition?
  - d. Even if you have to make a detailed plan?

3.) Change in perceived caring (i.e., "My current meals help to create a caring environment that helps me heal": Likert 1-5 scale: Strongly Disagree, Disagree, Neither Agree nor Disagree, Agree, Strongly Agree)

All answers to survey questions will be reported at baseline and follow-up in the PRO subpopulation. The change in responses to each survey question will be measured as the difference in score between follow-up and baseline responses. The proportion of participants with a decrease in isolation, increase in self-efficacy, or increase in perceived caring responses from baseline to follow-up will also be reported and compared using chi-squared tests.

A difference-in-differences approach will be used to compare the change in each survey question response by assigned group. The measure of association will be the coefficient (95% CI) for MTMs vs. Usual Care in linear regression models for each change in response adjusted for baseline differences in the PRO subpopulation.

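### Randomization is stratified by medical center, but the Cox, Fine-Gray and patient-reported outcome models leave center out; the cost is small and the repair is nearly free.

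*SAP*

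**What the plan says.** Protocol 7.4 names one stratification factor: "Pre-randomization will be stratified by participating KPNC medical center". There are five centers.

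The analysis plan does not return to it:

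- **SAP 3.3:** "an *a priori* decision was made to adjust for indices for acute severity of illness, predicted short-term readmission risk and multimorbidity burden", together with active Covid-19. Table 3-1, the list of candidate covariates, has no row containing center.
- **SAP 4.1, Cox:** the primary hazard ratio is "obtained from a Cox proportional hazards model adjusted for acute severity of illness, predicted short-term readmission risk and multimorbidity burden", with active Covid-19 and a catch-all, "along with any observed additional baseline differences in participant characteristics in the primary analysis population".
- **SAP 4.1, Fine-Gray:** the subdistribution hazard ratio is "obtained from Fine and Gray subdistribution hazard models adjusted for acute severity of illness, predicted short-term readmission risk and multimorbidity burden", with the same additions. The risk difference has a Wald interval and no stratification.
- **SAP 4.3:** changes in survey responses are compared in "linear regression models for each change in response adjusted for baseline differences in the PRO subpopulation", and proportions by chi-squared tests.
- **SAP 4.2 and 4.4:** both carry these methods over, to the secondary clinical outcomes and to the comparison of meals alone against meals with counseling.

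Neither document explains the omission.

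**The concern.** When patients are randomized within centers, the usual analysis compares arms within those centers. Here the only design factor is missing from the primary model and from every model built on it. If centers differ in readmission risk, a pooled Cox model estimates a hazard ratio pulled slightly toward 1. If allocation is blocked within center, the pooled test is also slightly conservative.

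The catch-all clause is not a dependable route back. The planned balance check uses the Table 3-1 variables, and center is not one of them. The clause also acts only when an imbalance is seen, whereas a design factor should be in the model whatever the data show.

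There is a second reason to care. Arms are assigned before manual eligibility review and consent (Protocol 6, 7.4 and 7.5), and SAP 3.1 analyzes only those who consented and left hospital alive. Stratifying the allocation therefore does not guarantee that arms are balanced by center among the patients analyzed.

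**Working it through.** **1. The plan's own figure.** SAP 2 states 80% power for a hazard ratio of 0.68 with N = 2000, a 10% event rate and two-sided alpha 0.05. The Schoenfeld formula is power = Φ(√d/2 × |ln HR| − 1.96), with |ln 0.68| = 0.3857.

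- 10% as the pooled rate: d = 200, so Φ(7.071 × 0.3857 − 1.96) = Φ(0.767) = 77.9%.
- 10% as the usual-care rate: d = 1000 × [0.10 + (1 − 0.90^0.68)] = 169.1, so Φ(6.502 × 0.3857 − 1.96) = Φ(0.548) = 70.8%.

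The stated 80% is not quite reached on either reading. That is a separate matter and does not depend on center. The simulation below treats 10% as the usual-care rate, so 70.8% is its benchmark.

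**2. Cox model with and without center.** The documents give neither center sizes nor center risks, so these are assumed: five centers of 400, 1:1 allocation in blocks of 8 within center, exponential times censored at 90 days, a common hazard ratio, no other covariates, and 4000 trials per scenario.

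| Center risks | Type I error, without / with center | Power at HR 0.68, without / with | Mean HR, without / with |
|---|---|---|---|
| all 10% | 4.8% / 4.8% | 70.8% / 70.8% | 0.677 / 0.677 |
| 6, 8, 10, 12, 14% | 4.8% / 5.0% | 70.0% / 70.3% | 0.679 / 0.678 |
| 3, 5, 10, 13, 19% | 4.5% / 5.1% | 68.8% / 70.0% | 0.685 / 0.681 |

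Monte Carlo error is about 0.3 points for type I error and 0.7 for power. In the last row the mean model standard error is 0.1569 with and without center, so the power difference comes from attenuation of the hazard ratio and not from a wider standard error.

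**3. Check on type I error.** With blocking, the pooled statistic has variance of about 1 − r, where r is the between-center share of outcome variance.

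- 6-14%: variance of risks 0.0008, r = 0.0008/0.09 = 0.009, type I error = 2[1 − Φ(1.96/√0.991)] = 4.9%.
- 3-19%: variance of risks 0.00328, r = 0.00328/0.09 = 0.036, type I error = 2[1 − Φ(1.96/√0.964)] = 4.6%.

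Both agree with the table. Without blocks the pooled test is nominal: a run with center risks of 3-17% and simple randomization gave 5.1% with and without center.

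**4. Linear models for patient-reported outcomes.** By the same argument under blocking, where the center-adjusted model has 80% power the unadjusted one has Φ(2.80 − 1.96/√(1 − r)).

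| r | Type I error without center | Power without center |
|---|---|---|
| 0.01 | 4.9% | 79.7% |
| 0.05 | 4.4% | 78.5% |
| 0.10 | 3.9% | 76.9% |

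The documents give no value of r.

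**5. If consent upsets center balance.** This is an illustration with assumed inputs: true hazard ratio 1, center risks 6-14%, and the share assigned to meals rising 45, 47.5, 50, 52.5, 55% in step with risk. Meals-arm risk = (0.45×6 + 0.475×8 + 0.50×10 + 0.525×12 + 0.55×14)/2.5 = 10.2%. Usual-care risk = (0.55×6 + 0.525×8 + 0.50×10 + 0.475×12 + 0.45×14)/2.5 = 9.8%. The apparent hazard ratio is ln(0.898)/ln(0.902) = 1.04. With a standard error of 0.142 the statistic shifts by 0.30, and type I error is about 6.0%. The pattern was deliberately aligned with risk; it shows a mechanism and does not forecast the trial.

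**The case against.** The strongest reply is that this is a convention with almost no consequence. Much of that stands. A loss of about one power point needs roughly a six-fold spread of risk across five centers of one health system, and no document suggests such a spread. The planned severity, readmission-risk and comorbidity scores would absorb whatever part of the center differences is case mix, and the simulation has no covariates, so it may overstate the gain. For the survey outcomes, the models use change scores, so stable center differences in level cancel, and SAP 2 expects more than 80% power even for small differences.

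Two stronger readings are tempting, and the documents do not support either.

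- **Standard errors are too large.** This depends on blocked allocation. Protocol 7.3 and 7.4 describe a program that randomizes within center and mention no blocks.
- **The meal vendor gives centers different baseline hazards.** Vendor does follow center: "Project Open Hand (POH) will provide MTMs service to patients enrolled at KP Santa Clara, Oakland and San Francisco Medical Centers", and the other vendor serves the remaining two. But Protocol 6 says usual-care participants get neither meals nor counseling from either vendor, so vendor cannot move their hazard. A vendor difference would be a difference in treatment effect, and a center-stratified Cox model with one hazard ratio does not address that. Vendor could shift a shared baseline only in the comparison of meals alone with meals plus counseling, which SAP 2 calls exploratory for utilization and survival.

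It is also fair that stratifying everywhere has a price. In the heart failure and diabetes subsets of SAP 4.4, few cause-specific events split over five strata can leave risk sets with only one arm, and these add no information.

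What the reply does not remove is an unexplained mismatch between design and primary model, in a trial where center balance among analyzed patients is not assured.

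**Conclusion.** The point holds as a minor one. Center is the only stratification factor and is absent from every planned model, and the catch-all does not reliably restore it. The expected cost in the Cox model is about 0 to 1 power point: none if centers have equal risk, 0.3 at 6-14% and 1.2 at 3-19%. Omission under a sound allocation does not inflate type I error. In the linear models the loss is 0.3 to 3.1 points for r from 0.01 to 0.10. All of this rests on assumed center risks, equal center sizes and a common hazard ratio, and the linear-model figures also assume blocking.

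A reader might infer that the primary result will be biased. The documents do not show that. Bias from this source needs differential consent or exclusion by arm and center, aligned with risk, and nothing in them indicates that it occurs. Including center guards against that one component; it does not repair other selection after randomization.

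**What to change.** In SAP 3.3, state that medical center enters all efficacy models as the stratification factor, whatever the observed balance. Then:

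- **4.1 and 4.2:** stratify the Cox models by center; use center as a stratum or fixed effect in Fine-Gray; replace the unstratified risk difference with a center-stratified Mantel-Haenszel one.
- **4.3:** add center as a fixed effect in the linear regressions.
- **4.4:** follow the same rule, but in the heart failure and diabetes meal subsets allow center as a fixed effect, or omit it where events are sparse, with the criterion written down beforehand.

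If the investigators prefer to leave center out, one sentence giving the reason would do. It would also help to state whether allocation is blocked within center.

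The cost is a few lines in the SAP and a change to the model statements. Center is already recorded, since randomization uses it. No new data and no change in sample size are needed. The change should be made before the outcome data are analyzed.
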